4.9.4 Vital Signs

Vital signs data, including weight, will be summarized for the actual values and the change from baseline value at each scheduled assessment.

Listings of vital signs data, including height and weight, will be provided.

4.9.5 ECOG Performance Status

ECOG performance status will be summarized at each scheduled assessment. Shift tables will summarize the shift from baseline to End of Treatment and to the worst post-baseline visit in ECOG performance status.

Listing of ECOG performance status will be provided.

4.9.6 Physical Examinations

Listing of physical examinations will be provided.

4.9.7 Pregnancy Test

Listing of pregnancy test results, if applicable, will be provided.

5 Final Analysis

All efficacy and safety endpoints will be analyzed and reported in the clinical study report (CSR). Results of PK analysis, immunogenicity analysis, [REDACTED] will be reported separately.

6 Data handling conventions

6.1 General conventions

6.1.1 Missing data

In general, missing data including dates will be treated as missing and no data imputation will be applied, unless otherwise specified. Data that are potentially spurious or erroneous will be queried and examined during the review of the study data.

If there are partial or missing dates for an AE, then it will be considered as a TEAE. If the assessment of the relationship of an AE to study drug is missing, then the relationship will be as possibly related.

If the severity/grade is missing for one of the treatment emergent occurrences of an AE, the maximal severity of the remaining occurrences will be considered. If the severity is missing for all the occurrences a “missing” category will be added in summary table.

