3 STUDY OBJECTIVES AND ENDPOINTS

Study objectives and associated endpoints are presented below in [Table 3](#).

Table 3. Study Objectives and Endpoints

Objectives	Endpoints
Primary	
Characterize the safety and tolerability of camidanlumab tesirine as monotherapy and camidanlumab tesirine in combination with pembrolizumab, and to identify the recommended dose(s) and schedule(s) for future studies in patients with selected advanced solid tumors	
Frequency and severity of adverse events (AEs) and serious adverse events (SAEs) for patients treated with camidanlumab tesirine as monotherapy and for patients treated with camidanlumab tesirine in combination with pembrolizumabChanges from Baseline of safety laboratory values, vital signs, Eastern Cooperative Oncology Group (ECOG) performance status, and 12-lead electrocardiograms (ECGs) for patients treated with camidanlumab tesirine as monotherapy and for patients treated with camidanlumab tesirine in combination with pembrolizumabFrequency of dose interruptions and dose reductions for patients treated with camidanlumab tesirine as monotherapy and for patients treated with camidanlumab tesirine in combination with pembrolizumabIncidence of dose limiting toxicities (DLTs) (dose-escalation only) for patients treated with camidanlumab tesirine as monotherapy and for patients treated with camidanlumab tesirine in combination with pembrolizumab
Secondary	

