4.2 Study Periods

4.2.1 Screening Period

Informed consent must be obtained for each patient and documented with a signed informed consent form (ICF) prior to any study procedures. Procedures that are performed as part of standard of care (SoC) may be used to satisfy screening requirements if they are performed in the appropriate window.

The screening period is from 21 days to 1 day prior to the start of the study drug. The screening assessments should be performed within this period in order to assess the eligibility of the patient against the inclusion and exclusion criteria (Sections 5.1 and 5.2, respectively).

See Section 5.3 for the information to be collected on screening failures.

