8.1.1 Adverse Events of Special Interest

For this study the following AEs, irrespective of seriousness and causality, are considered AESIs (except those clearly attributed to pembrolizumab alone):

- GBS (including variants such as acute motor and sensory axonal neuropathy)
- Polyradiculopathy
- Autonomic nervous system imbalance
- Nerve palsy
- \geq Grade 3 neurologic toxicities
- \geq Grade 3 immune-mediated toxicities. Of note, rashes will not be considered as immune-mediated skin toxicities, since they are well described toxicities of PBD-dimers; with exception for Stevens-Johnson syndrome, toxic epidermal necrolysis, acute generalized exanthematous pustulosis, exfoliative dermatitis, and drug reaction with eosinophilia and systemic symptoms (Note: immune-mediated skin toxicities will need confirmatory skin biopsy)

- Autoimmune-mediated events (such as, but not limited to, pneumonitis, hepatitis, colitis, endocrinopathies, type 1 diabetes mellitus, and nephritis/renal dysfunction)

For all AESIs it is important to provide as much information as possible: e.g., time of onset (including changes in severity), duration of events, time to resolution, and relationship to camidanlumab tesirine. It is also important to specify if any AEs are autoimmune mediated.

Adverse events of special interest will be closely monitored and followed.

8.2 Eliciting and Reporting Adverse Events/Adverse Events of Special Interest/Serious Adverse Events

Patients will be instructed to contact the Investigator at any time after ICF signature if any symptoms develop. At each study visit, patients will be asked a non-leading question to elicit any medically related changes in their well-being. Patients may also report AEs voluntarily and they will be instructed to contact the Investigator between visits if any symptoms develop or worsen.

All AEs will be reported starting when the patient provides written informed consent. Clinically significant medical conditions present at the time of ICF signature will be reported as medical history. Clinically significant medical conditions that start or worsen after ICF signature will be reported as AEs.

All AEs, AESIs, and SAEs, regardless of relationship to study drugs (camidanlumab tesirine and pembrolizumab), will be reported from the time the patient signs the ICF until 30 days after the last dose of study drug; thereafter, only related SAEs will be reported.

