4.9.1 Adverse Events

4.9.1.1 Analyses of Adverse Events

An AE is defined as any untoward medical occurrence in a patient or clinical investigation subject administered a pharmaceutical product, which does not necessarily have to have a causal relationship with this treatment.

The definition of SAEs is referred to the Protocol section 8.1.

A treatment-emergent AE (TEAE) is defined as an AE that occurs or worsens in the period extending from the first dose of study drug to 30 days after the last dose of study drug in this study or start of a new anticancer therapy, whichever is earlier.

AEs will be coded according to MedDRA Version 22.0, and the severity of the toxicities will be graded according to the National Cancer Institute (NCI) Common Terminology Criteria for Adverse Events (CTCAE) Version 4.0, where applicable.

The summary of overall TEAEs includes:

- TEAEs
- Drug-related TEAEs
- Grade ≥ 3 TEAEs
- Drug-related Grade ≥ 3 TEAEs
- Serious Adverse Events (SAEs)
- Drug-related SAEs
- TEAEs leading to dose delayed, reduced or interrupted (camidanlumab tesirine or pembrolizumab)
- TEAEs leading to discontinuation of camidanlumab tesirine or pembrolizumab
- TEAEs leading to death
- Infusion related reactions

The incidence of TEAEs will be summarized by system organ class (SOC) and preferred term (PT). A subject will be counted only once within a SOC and PT, even if the subject experienced more than one AE within a specific SOC and PT. Below TEAEs will be summarized in the same fashion:

- Drug-related TEAEs by SOC and PT
- Grade ≥ 3 TEAEs by SOC and PT
- Drug-related Grade ≥ 3 TEAEs by SOC and PT
- The most common TEAEs ($\geq 10\%$ incidence) by PT
- TEAEs by SOC, PT and maximum CTCAE grade
- TEAEs by relationship to study drug, maximum CTCAE grade, SOC and PT

Listing of all AEs, including non-TEAEs, will be provided. Besides, TEAEs leading to dose reduced, delayed or interrupted (camidanlumab tesirine or pembrolizumab), TEAEs leading to discontinuation of camidanlumab tesirine or pembrolizumab, and TEAEs leading to death will also be provided.

Details on classification of AEs with missing or partial onset dates are provided in Section 6.

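### The SAP counts an adverse event with an incomplete date as treatment-emergent even when the known part of the date proves that it began before first dose

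*SAP*

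**What the plan says.** SAP 4.9.1.1 gives the definition: "A treatment-emergent AE (TEAE) is defined as an AE that occurs or worsens in the period extending from the first dose of study drug". The window closes 30 days after the last dose or when a new anticancer therapy starts, if that is earlier. Protocol 9.8.1 has the same definition and makes TEAEs the focus of the AE summaries.

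For incomplete dates, SAP 4.9.1.1 points onward: "Details on classification of AEs with missing or partial onset dates are provided in Section 6". The only rule found there, in SAP 6.1.1, is: "If there are partial or missing dates for an AE, then it will be considered as a TEAE". The same section sets the general convention: "In general, missing data including dates will be treated as missing and no data imputation will be applied, unless otherwise specified". Nothing in either document tells the programmer to compare a known month, year or end date with the date of first dose.

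On collection, Protocol 8.2 says: "All AEs will be reported starting when the patient provides written informed consent". On timing, Protocol 4.2.1 says: "The screening period is from 21 days to 1 day prior to the start of the study drug".

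**The concern.** A default to TEAE is sensible when the data cannot place an event. This rule applies the default even when the data can place it. An event dated only to a month that ended before first dose is a pre-treatment event under the SAP's own definition, unless it later worsened, and SAP 6.1.1 still counts it as a TEAE.

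AE and SAE frequency and severity come first among the primary endpoints in Protocol Section 3, and the TEAE tables are how that endpoint is mainly reported. The tables are split by dose level, and the escalation cohorts are small. A single misplaced record can therefore be visible in a preferred-term or Grade 3 and above row, at the point where dose levels are read against each other.

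**Working it through.** The plan states no figure on this point, so there is none to reproduce. The check has three parts.

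**1. The rule against the definition.** The first two rows use an illustrative first dose on 10 March 2021.

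| AE record | What the known part shows | TEAE definition | SAP 6.1.1 |
|---|---|---|---|
| Onset February 2021, day unknown | Latest possible onset is 28 February, before first dose | Not a TEAE unless it worsened after dosing | TEAE |
| Onset March 2021, day unknown | May be before or after first dose | Cannot be applied | TEAE |
| Onset missing, end date before first dose | Began and ended before dosing, so cannot have worsened on treatment | Not a TEAE | TEAE |
| Onset fully missing, no end date | Nothing | Cannot be applied | TEAE |
| Onset month wholly after the TEAE window | Too late | Not a TEAE | TEAE |

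Rows 2 and 4 are a reasonable conservative default. Rows 1, 3 and 5 are the conflict.

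Row 5 is rare. Under Protocol 8.2, only related SAEs are reported once 30 days have passed since the last dose. What remains is those late SAEs, plus events that follow an early switch to a new anticancer therapy.

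**2. How often month and year alone would decide (illustration).** Let L be the days from consent to first dose, and let first dose fall on day d of a month. The number of pre-dose days in an earlier month is max(0, L + 1 − d). For L up to 21, this sums to L(L + 1)/2 over a month. Assume that first-dose dates are spread evenly over 2019 to 2021, which is 36 months and 365 + 366 + 365 = 1,096 days. Then

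share = 36 × [L(L + 1)/2] / (1,096 × L) = 18(L + 1)/1,096.

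- L = 21: 18 × 22/1,096 = 0.361, about 36%
- L = 14: 18 × 15/1,096 = 0.246, about 25%
- L = 7: 18 × 8/1,096 = 0.131, about 13%

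These are shares of pre-dose days, not of AEs. If pre-dose onsets were spread evenly over a 21-day screening period, about 36% of those recorded with the day missing would be provably pre-dose.

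**3. Largest effect of one patient on an incidence, 100/n.**

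| Group | n | Points |
|---|---|---|
| Escalation cohort (Protocol 4.1.1) | 3 | 33.3 |
| Escalation cohort, expanded | 6 | 16.7 |
| Dose level with added patients (Protocol 4.1.1) | 10 | 10.0 |
| Expansion Group 2 (Protocol 4.1.2) | 14 | 7.1 |
| Expansion Group 1 (Protocol 4.1.2) | 16 | 6.25 |

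These are ceilings. A patient counts once per system organ class and preferred term (Protocol 9.8.1, SAP 4.9.1.1), so a cell moves only if the patient has no other TEAE in it. For the row of patients with any TEAE, the effect is likely to be close to nil: in ADCT-301-001, 132 of 133 patients had one (Protocol 1.3.1).

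**The case against.** The best defence is that an inclusive default is a proper safety choice. It can overstate toxicity but cannot hide it. Onset date is a required AE field (Protocol 8.2), so incomplete dates should be few after data cleaning. No hypothesis is tested, and all AEs are listed, including non-TEAEs, so a pre-dose record can be found. Worsening also counts, and Protocol 8.3 does not require each episode of an intermittent AE to be documented, so a pre-dose onset does not always settle the matter.

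Most of this stands, and it limits the size of the point. It does not remove it. Listings do not correct the summary tables. The query sentence in SAP 6.1.1 covers spurious or erroneous data and does not name partial dates. The defence of an inclusive default applies to undecidable dates, not to dates that decide.

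A reader might infer more than the documents support:

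- **Every ongoing pre-dose AE becomes a TEAE because its end date is missing.** SAP 6.1.1 does say only dates, but SAP 4.9.1.1 refers to it for onset dates. Protocol 8.2 records an unresolved AE as ongoing, which is a status and not a missing date.
- **The rule contradicts the TEAE definition throughout.** It does so only where the known part of the date decides.
- **Pre-treatment events will be tabulated as drug-related.** The rule that sets missing causality to possibly related makes this possible, but it needs a second gap in the same record, and causality is also a required field.
- **Dose escalation or study stopping is affected.** Dose-limiting toxicities have their own definition and 21-day period (Protocol 6.5). One stopping criterion in Protocol 4.3 does refer to treatment-emergent AEs, but neither document says that the SAP date rule feeds that decision.

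**Conclusion.** The point holds, with limited reach. SAP 6.1.1 is a stated rule, not a missing detail. It misclassifies AEs whose known onset month or year, or known end date, proves that they began before first dose without later worsening. It also misclassifies, more rarely, those known to start after the TEAE window. The affected tables are the main summary of a primary endpoint.

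The frequency cannot be derived from the documents and is probably small. The direction is known: TEAE incidence can only be overstated. The 33 and 17 points for cohorts of 3 and 6 are upper limits for one patient in one cell, and should not be read as typical. Dose levels in the Safety Analysis Set can be larger, through paired-biopsy patients (up to 3 per level) and added patients (Protocol 4.1.1). In the expansion groups the limit is 6 to 7 points. The calendar shares rest on evenly spread first-dose and onset dates and are only an illustration.

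**What to change.** Replace the sentence in SAP 6.1.1 with:

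*An AE with a partial or missing onset date is classified as a TEAE unless the known parts of the onset date, or a known end date, show that it began before first dose without recorded worsening on or after first dose, or that it began after the TEAE window. Fully missing or undecidable onsets, and events whose worsening status cannot be determined, remain TEAEs.*

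The word *onset* brings the rule into line with the cross-reference in SAP 4.9.1.1. No imputation is needed: the programmer compares the latest possible onset date with first dose, and the earliest possible onset date with the end of the window.

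The cost is one SAP sentence and routine code. No stated figure in the plan changes. The one small downside is that worsening may be undocumented for intermittent AEs, and the last clause covers this by keeping those events as TEAEs.

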6.1.2 Unscheduled visits

Unscheduled visit measurements of laboratory data, vital signs, and ECG will be used for computation of baseline and worst values and/or grades. Re-windowing for unscheduled visits will not be performed.

6.1.3 Duplicated visits

Depending on the statistical analysis method, single values may be required for each analysis window. For example, change from baseline by visit usually requires a single value per visit. Unless otherwise noted throughout the rest of this document, when a single value is needed, the following rule(s) will be used:

- If more than 1 assessment occurs during the same nominal visit, select the record closest to the nominal day for that visit.
- If there are 2 assessments that are equidistant from the nominal day, the data of the assessment after the scheduled study day will be used.
- The last measurement will be used if multiple measurements are taken on the same day.

7 Reference List
